7.2. Treatment Period (Cycle 1 - 4)

Patients will be hospitalised during at least the first three days of the first cycle and during at least the first two days of each following cycle. Before starting the infusion of blinatumomab, the patient will be examined physically and blood samples for safety laboratory parameters will be taken. For starting the study treatment the laboratory results will not have to be awaited.

Following the start of the infusion AE/SAE and concomitant medication will be evaluated continuously throughout the whole study until the 90-day visit. After the 90-day visit, only (S)AEs potentially related to blinatumomab should be documented in the CRF (and reported to the sponsor, if applicable). In addition, only anti-leukemic concomitant medication and medication related to blinatumomab related (serious) adverse events should be documented in the CRF. The vital signs and the laboratory tests will be repeated on D2 and D3 and at each visit during the treatment period.

Replacement of infusion bags will be performed as described in the Operations Manual. CADD pump infusion bags will be changed twice a week. To account for weekends and bank holidays, this will be on Tuesdays and Fridays. Each treatment cycle should begin on a Tuesday.

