7.3. Follow-up Period

7.3.1. 90-day Safety Follow-up Visit

A Safety follow-up visit will be performed at 90 days after the end of infusion with blinatumomab. In case an allogeneic HSCT is planned following treatment with blinatumomab, the 90-day Safety Follow-Up Visit should be performed at the latest possible timepoint prior to the initiation of transplant conditioning, even if the 90 days have not elapsed. This visit will also be documented as End-of-Core-Study Visit and the following procedures and tests will be performed:

- Physical examination and ECOG performance status
- Neurological examination
- Writing test
- Vital signs/temperature
- 12-lead ECG
- Routine bloods, U/E, LFTs, LDH, Coagulations screen, FBC (aproximately 30mL of blood)
- Urinalysis
- Pregnancy test (in women of childbearing potential)
- Serum immunoglobulins (IgG)
- Concomitant medication
- AE/SAE assessment

7.3.2. 2-Year Efficacy Follow-up Period

For patients who did not undergo allogeneic HSCT, Efficacy follow-up visits for assessment of molecular relapse and until haematological relapse will take place 3-monthly (calculated from cycle 1 day 1) within the first year and 6-monthly within the second year until completion of a 2-year period after treatment with blinatumomab. The following procedures and tests will be performed:

- Physical examination and ECOG performance status
- Vital Signs/Temperature
- Bone marrow aspirate/biopsy
- Routine bloods, U/E, LFTs, LDH, Coagulations screen, FBC (aproximately 30mL of blood)
- Urinalysis
- Recording of anti-leukemic concomitant medication
- Recording of AE possibly related to blinatumomab

For patients who underwent allogeneic HSCT the investigator will contact the patients or his/her treating physician (e.g. via phone) to receive information concerning haematological relapse free and overall survival. Also, information concerning the conditioning regimen, donor type and 100d HSCT related mortality will be collected in the CRF. In addition to the routine collection of adverse events within the core study and until 90 days after last administration of study medication, investigators will report adverse events possibly related to blinatumomab thereafter.

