7.4. Unscheduled Visits

Unscheduled visits should be performed whenever necessary, i.e. in case of adverse events or in case of symptoms of clinical disease progression. Evaluations and/or assessments will be performed, as deemed appropriate by the investigator based on the nature of the event. Results will be documented in the patient's file and recorded in the CRF. If a patient is withdrawn from the study, efforts should be taken to perform all examinations scheduled for the End-of-Core-Study visit (please see section 7.5.1, 30-day Safety Follow-up Visit).

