8.3. Bone Marrow Aspiration

Evaluation of MRD will be performed on bone marrow aspirate samples. Each bone marrow will be evaluated for presence of leukaemia cells with differential count by light microscopy at the local laboratory and results entered on the CRF.

At the end of the first treatment cycle (D29) a bone marrow aspiration will be performed and shipped to the central MRD laboratory for the evaluation of the primary endpoint. In case of technically suboptimal samples (i.e. *ABL* Ct >26), a second bone marrow aspiration will be performed to confirm whether the primary endpoint of complete molecular response was reached or not.

At the end of each treatment cycle (D29) and during the efficacy follow-up visits a bone marrow aspiration will be performed to evaluate MRD and morphology defining the percentage of leukemic blasts in bone marrow. Furthermore, in the event of abnormal blood counts (suggesting leukemic relapse), a bone marrow evaluation should be performed prior to initiating the subsequent cycle of treatment with blinatumomab.

Additional tests conducted by the investigators but not required by protocol such as immunophenotypic, cytogenetic or molecular analyses during the study will be collected and documented in the CRF. During the study, haematological/morphological assessments of the bone marrow will be performed locally.

9. Assessment of Safety

Adverse events (AEs) will be reported from the time of consent up to ninety days after the completion of the final dose of Blinatumomab.

All serious adverse events (SAEs) must be reported immediately (and within 24 hours of knowledge of the event) by the PI at the participating site to the Clinical Trials Office (CTO).

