9.5. Reporting procedures

Death as a result of disease progression and other events that are primary or secondary outcome measures are not considered to be SAEs and should be reported in the normal way, on the appropriate CRF.

The PI (or delegated medically qualified doctor from the trial team) should sign and date the SAE report to acknowledge that he/she has performed the seriousness and causality assessments. Investigators should also report SAEs to their own trust in accordance with local practice.

All SAEs, SARs and SUSARs (excepting those specified in this protocol as not requiring reporting) will be reported immediately (and certainly no later than 24hrs) by the Investigator to the KHP-CTO and CI for review in accordance with the current Pharmacovigilance Policy.

The participant will be identified only by trial number, date of birth and initials. The participant's name should not be used on any correspondence.

It is also required that sites respond to and clarify any queries raised on any reported SAEs and report any additional information as and when it becomes available through to the resolution of the event. Additionally, the KHP-CTO and Amgen may request additional information relating to any SAEs/SARs and the site should provide as much information as is available to them in order to resolve these queries.

Serious Adverse Event (SAE) email address:

[contact]

Adverse events should be reported from the time of signature of informed consent, throughout the treatment period up to, and including 90 days after the participant receives their last dose of the IMP. Serious adverse reactions (such as long-term side effects of trial treatment under investigation) should continue to be reported until the end of follow up.

Adverse events (AE) should be graded using the NCI Common Terminology Criteria for Adverse Events (CTCAE) Version 5.0. The toxicity grades should be recorded on the toxicity part of the CRF.

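### Section 7.2 ties full adverse event recording to a 90-day visit that 7.3.1 brings forward for transplant patients, contradicting the fixed 90-day window stated elsewhere

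*Protocol*

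**What the plan says.** Section 7.2 sets the end of full recording by a visit: "Following the start of the infusion AE/SAE and concomitant medication will be evaluated continuously throughout the whole study until the 90-day visit". It then narrows what is kept: "After the 90-day visit, only (S)AEs potentially related to blinatumomab should be documented in the CRF".

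Section 7.3.1 places that visit 90 days after the end of infusion, with an exception. If an allogeneic transplant is planned, the visit "should be performed at the latest possible timepoint prior to the initiation of transplant conditioning, even if the 90 days have not elapsed". The visit is also labelled the End-of-Core-Study Visit.

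Four other places set the limit by the calendar:

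- The schedule of events continues the adverse event row for 90 days once treatment has stopped.
- The opening of section 9 states: "Adverse events (AEs) will be reported from the time of consent up to ninety days after the completion of the final dose of Blinatumomab".
- Section 9.5 has reporting run from the signing of consent "throughout the treatment period up to, and including 90 days after the participant receives their last dose of the IMP".
- The last sentence of section 7.3.2, in the paragraph on transplanted patients, has routine collection continue "until 90 days after last administration of study medication, investigators will report adverse events possibly related to blinatumomab thereafter".

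For withdrawn patients, section 7.4 asks for the End-of-Core-Study examinations and adds: "please see section 7.5.1, 30-day Safety Follow-up Visit".

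**The concern.** For a patient whose visit takes place on time, the visit rule and the calendar rule give the same end date. For a patient going to transplant they do not, and a site cannot follow both. Section 5.5 allows transplant in place of further cycles after at least one cycle, so this is a planned route through the trial.

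If a site follows 7.2, any event between the brought-forward visit and day 90 reaches the database only if someone already suspects blinatumomab. Full collection up to day 90 exists so that recording does not depend on that judgement. Section 10.2 reports adverse event and serious adverse event incidences for each patient and cycle, and section 10 monitors excessive toxicity through this same visit. With at most 17 patients, unequal observation of a few can shift those incidences and make transplanted and non-transplanted patients hard to compare.

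**Working it through.** **Step 1: compare the stopping rules.**

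- Visit rule (7.2 with 7.3.1): full recording stops at the visit, which may fall before day 90 when a transplant is planned.
- Calendar rule (schedule of events, 9, 9.5, end of 7.3.2): full recording stops 90 days after the last dose or after treatment stops, whenever the visit took place.

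Nothing in the protocol says which rule governs when the visit is brought forward.

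**Step 2: ask whether the calendar rule can be carried out after transplant.** For transplanted patients, section 7.3.2 replaces clinic visits with contact, for example by telephone. The items it lists are haematological relapse-free and overall survival, conditioning regimen, donor type and 100-day transplant-related mortality. A full adverse event enquiry up to day 90 is not among them, and the contact has no stated date. The closing sentence of 7.3.2 assumes routine collection to day 90 without naming the contact that would deliver it.

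**Step 3: size the gap under the visit rule.** Let v be the number of days from the end of infusion to the brought-forward visit. Days of full collection lost = 90 − v. The protocol does not give the conditioning date, so v is an assumption:

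- v = 14 (day 43 of a cycle whose infusion ends on day 29): 90 − 14 = 76 days, 76/90 = 84%.
- v = 21: 90 − 21 = 69 days, 69/90 = 77%.
- v = 56: 90 − 56 = 34 days, 34/90 = 38%.

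Under the calendar rule the loss is 0 days for every v.

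**Step 4: how many patients.** The protocol gives no expected transplant rate. The only figure it quotes is 57%, from the AML17 relapse arm (section 3), which is a different population given salvage chemotherapy. Over an assumed range of 20% to 57%: 0.20 × 17 = 3.4 and 0.57 × 17 = 9.7, or about 3 to 10 patients if the trial reaches 17.

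**Step 5: which results are exposed.** The secondary toxicity endpoint counts grade 3 or worse non-haematological events in the first cycle. A cycle lasts six weeks, so with infusion ending on day 29, any visit 14 or more days later falls at or after day 43 (29 + 14), when cycle 1 has closed. Only conditioning begun inside the infusion-free interval could cut into that endpoint. The exposure lies mainly in the overall adverse event tables and in the toxicity monitoring described in section 10.

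**Step 6: the reference in 7.4.** The protocol has no section 7.5.1 and no 30-day visit. The End-of-Core-Study Visit that 7.4 names is the one in section 7.3.1, at 90 days.

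**The case against.** The best defence is that four statements give the calendar limit and only 7.2 gives the visit limit. Section 9 is the safety section, and the closing sentence of 7.3.2 sits in the paragraph on transplanted patients and names both the core study and the 90 days. On that view, 7.2 is shorthand for the usual case. A last assessment before conditioning is also sensible, because conditioning toxicity would obscure anything seen later.

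Much of this stands. It means the window is contradictory, not settled as short. It does not remove the conflict: 7.2 is the section that tells sites what to enter in the CRF during and after treatment, and 7.3.2 lists no enquiry that would deliver the calendar rule.

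A reader might infer more than the text supports:

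- **That collection ends at the brought-forward visit.** It narrows. Potentially related events are still recorded (7.2, 7.3.2), and serious adverse reactions are reported to the end of follow-up (9.5).
- **That withdrawn patients are followed for only 30 days.** Section 7.4 says which examinations to attempt and carries a wrong cross-reference; it sets no limit on adverse event collection. Section 6.6 provides a withdrawal visit and follows a serious reaction for as long as it lasts. No loss of days can be calculated for these patients.
- **That the start of collection conflicts in the same way.** Sections 9 and 9.5 say from consent. Section 7.2 speaks of the period after infusion starts, but it opens the treatment section and does not exclude earlier events. The schedule's adverse event row does not mention consent.
- **That the shortfall is tied to response.** Section 5.5 requires only suitability for transplant. Section 3 says that MRD informs transplant timing in current practice, so a link is plausible, but the protocol does not state one.

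**Conclusion.** The point holds as an internal contradiction affecting patients who go to transplant. Sections 7.2 and 7.3.1 together narrow adverse event recording before day 90, while the schedule, section 9, section 9.5 and the end of 7.3.2 keep it open to day 90. Under 7.2, about 38% to 77% of the 90-day window is lost if the visit falls 56 to 21 days after infusion, and more if it falls sooner; under the calendar rule none is lost. These figures rest on assumed conditioning dates, and the estimate of 3 to 10 affected patients rests on an assumed transplant rate. The primary endpoint is untouched and the cycle 1 toxicity endpoint largely so. The wrong reference in 7.4 is a separate, minor error that needs correcting but does not shorten anyone's safety follow-up. The wording should be aligned, because the correction is specific and inexpensive.

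**What to change.** 1. In section 7.2, replace the visit as the end of full recording with the window in sections 9 and 9.5: from consent until 90 days after the last dose, whether or not the 90-day visit has been brought forward. The restriction to potentially related events should begin after that date.
2. In section 7.3.2, add to the contact for transplanted patients an enquiry about all adverse events and serious adverse events covering the period up to day 90 after the last dose. The contact has no stated date, so one must be set on or soon after day 90.
3. Tabulate events that start after conditioning separately from those before it.
4. In section 7.4, correct the reference to section 7.3.1, 90-day Safety Follow-up Visit.

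The cost is a few wording changes and one dated enquiry for each transplanted patient. The downside is that some transplant-related events will be recorded; the separate table keeps them from obscuring the events before conditioning.

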4.3. Secondary endpoints

- Incidence of patients experiencing a grade 3 or greater non-haematological toxicity during the first cycle of treatment.
- Incidence of molecular complete remission at any time from trial entry (evaluated at end of trial)
- Molecular relapse free survival time (evaluated at end of trial)
- Overall survival time (evaluated at end of trial)
- Number of days of hospital admission at 1, 3 and 6 months from entry
- Number of days on intravenous antibiotics or antifungals at 1, 3 and 6 months
- Number of blood components infused at 1, 3 and 6 months

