4.5. Schedule of events

	Screening (within 21							Cycl	es 1 to	4					90 days	2-Year Follow-	NACAL -I
	days prior to treatment)	Day 1*§	Day 2§	Day 3	Day 4	Day 8 (+/- 2d)	Day 11	Day 15 (+/- 2d)	Day 18	Day 22 (+/- 2d)	Day 25	Day 29 (+/- 2d)	Days 30-42 (+ 7d)	Unschedule d visit	after last treatment (+/- 5d)	up Period ^	Withdrawal visit
Informed consent	X																
Eligibility assessment	Х																
Medical history	Х																
Physical exam,vital signs and temperature	х	х	х	Х		Х		Х		Х		Х		Х	Х	Х	х
Neurological exam and writing test	Х	Х	Х	Х		Х		Х		Х		Х		Х	Х		Х
ECOG performance status	Х															Х	
ECG	Х														Х		Х
Urinalysis	Х	Х	Х	Х		Х		Х		Х		Х			Х	Х	Х
Pregnancy test (if applicable)	Х														Х		Х
Haematology and biochemistry	Х	Х	Х	Х		Х		Х		Х		Х		Х	Х	Х	Х
Virology (HIV, HBV, HCV)	Х																
Serum immunoglobulins	Х											Х			Х		Х

	' after last													2-Year Follow-	With drawal		
	days prior to treatment)	Day 1*§	Day 2§	Day 3	Day 4	Day 8 (+/- 2d)	Day 11	Day 15 (+/- 2d)	Day 18	Day 22 (+/- 2d)	Day 25	Day 29 (+/- 2d)	Days 30-42 (+ 7d)	Unschedule d visit	treatment (+/- 5d)	up Period	Withdrawal visit
Bone Marrow aspirate (+/- trephine)	Х											X ⁺				Х	
Response assessment												Х					
Blinatumomab infusion			Continuous infusion days 1 – 28 of each cycle Treatment break														
CADD pump attendance#		х			х	х	х	х	х	х	х	х					
Concomitant medications	Х		<< Ongoing assessment >>														
Adverse events			<< Ongoing assessment until 90 days after treatment discontinuation >>								X						
Supportive Care Requirements						<<	Ongoi	ng assessi	ment ur	ntil treatme	nt disco	ontinuation	>>				Х

NOTES:

Data on concomitant medications, adverse events and supportive care requirements may be collected during unscheduled visits

[figure not shown]
§ indicates inpatient visits. All other scheduled visits are outpatient visits.

*Clinical assessments and laboratory assessment performed within 3 days prior to the first dose of blinatumomab will not have to be repeated on day 1 cycle 1

^For patients who did not undergo allogeneic HSCT, Efficacy follow-up visits for assessment of molecular relapse and until haematological relapse will take place 3-monthly (calculated from cycle 1 day 1) within the first year and 6-monthly within the second year until completion of a 2-year period after treatment with blinatumomab. Telephone follow-up will be performed for patients who have undergone HSCT.

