5.5. Dosing Regimen

Patients will receive one to four consecutive cycles of blinatumomab. A cycle consists of a continuous intravenous infusion at a dose of 28 mcg/day over four weeks followed by an infusion free interval of two weeks. Patients will receive four cycles of treatment, unless criteria for treatment discontinuation apply. The duration of one cycle is 6 weeks, including a four week continuous intravenous infusion and a two week infusion free interval, which may be extended by a maximum of 7 days. In case of haematological relapse, the study treatment will be permanently discontinued. Patients are generally are expected to receive four cycles of treatment, independently from achieving complete molecular response. If patients are suitable for allogeneic HSCT after treatment with at least one treatment cycle of blinatumomab, they may undergo allogeneic HSCT instead of receiving further cycles with blinatumomab. Following the last treatment cycle, there will be a safety follow-up visit at 90 days after last infusion, documented as End-of-Core-Study Visit, followed by efficacy follow-up visits at three, six, nine, 12, 18 and 24 months after treatment start. Efficacy follow-up visits at six months will only be applicable for patients completing less than 4 cycles, at three months only for patients having completed 1 cycle only.

After completion of the two year efficacy follow-up period, information concerning haematological relapse free, leukaemia treatment free and overall survival as well as further data on hospitalisation and the use of relevant anti-leukemic, antibiotic, and antifungal medication and transfusion of blood products, and hospitalisation, if available, will be gathered by telephone at least every six months until death or at least until five years after treatment start, whichever occurs earlier. Patients who discontinue treatment prematurely

will enter immediately the efficacy and/or survival follow-up study. Patients who discontinue treatment before completion of the first treatment cycle will be assessed for MRD response on day 29 (and day 43, if applicable) of cycle 1 before entering the efficacy and/or survival follow-up study. In case of haematological relapse within the treatment period, treatment will be terminated at the time of relapse.

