5.14. Concomitant Medication

The following medication and therapies will be prohibited during the study until end of the efficacy period:

- Any anti-tumour therapy other than the investigational product i.e. cytotoxic and/or cytostatic drugs, radiation therapy or immunotherapy.
- Any other investigational agent
- Chronic systemic high-dose corticosteroid therapy (i. e. > 20 mg prednisone daily)
- Any other immunosuppressive therapies (except for protocol mandated interventional corticosteroids)
- Non-steroidal anti-inflammatory drugs (NSAIDs, except for paracetamol and naproxen)
- Tyrosine kinase inhibitors

For management of concomitant therapies, please refer to the Investigators Brochure. A complete listing of all concomitant medication received during the treatment phase must be recorded in the relevant CRF. This will include all medications at baseline and any changes during the treatment period.

6. Selection and Withdrawal of Participants

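### Scheduled collection of supportive care and anti-infective use ends before the 3- and 6-month resource-use counts are complete, most of all in patients who stop early or go to transplant

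*Protocol*

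**What the plan says.** Resource utilisation is a secondary objective (Section 4.1). Section 4.3 turns it into three endpoints. The one for inpatient stay is "Number of days of hospital admission at 1, 3 and 6 months from entry". The one for anti-infective treatment is "Number of days on intravenous antibiotics or antifungals at 1, 3 and 6 months". The one for transfusion is "Number of blood components infused at 1, 3 and 6 months". Only the first names its time origin.

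The collection rules are spread over several sections:

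- Section 4.5: the row "Supportive Care Requirements" is assessed on an ongoing basis up to discontinuation of treatment, with a further mark at the withdrawal visit. The adverse-event row beside it runs for 90 days longer.
- Section 5.14: "A complete listing of all concomitant medication received during the treatment phase must be recorded in the relevant CRF".
- Section 7.2: concomitant medication is followed to the 90-day visit. After it, "only anti-leukemic concomitant medication and medication related to blinatumomab related (serious) adverse events should be documented in the CRF".
- Section 7.3.1: for a patient going to allogeneic transplant, the 90-day visit is held before conditioning, even if 90 days have not passed.
- Section 7.3.2: the only medication item at the efficacy visits is "Recording of anti-leukemic concomitant medication". Contact after transplant covers relapse, survival, conditioning regimen, donor type and 100-day mortality.
- Section 5.5: once the two-year follow-up is over, telephone contact gathers survival information "as well as further data on hospitalisation and the use of relevant anti-leukemic, antibiotic, and antifungal medication and transfusion of blood products", where available.
- Section 8.2: the three resource endpoints are assessed by reviewing CRFs and patient medical notes. No period is given.

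**The concern.** The endpoints are cumulative counts over fixed calendar windows, while the scheduled collection is tied to treatment. A patient who stops after one cycle leaves the supportive-care row at about one month but is still due a 3- and a 6-month count.

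The length of the uncovered time depends on outcome. It is longest in patients who stop for relapse, toxicity or transplant, who plausibly go on to need more beds, blood and intravenous drugs. Any use that goes unrecorded lowers the count. The trial has one arm, and Section 3 offers published FLAG-Ida figures for inpatient stay, transfusion and antibiotic days, so readers will naturally set the trial's counts against those. A statistical analysis plan could not repair this afterwards, because it cannot recover data that were never collected.

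**Working it through.** The protocol gives no figure for this point, so there is none to reproduce. The check is calendar arithmetic.

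**Inputs.** A cycle is 28 days of infusion plus a 14-day interval, which may be extended by up to 7 days (Section 5.5). Disconnection is on day 29 (Sections 4.5 and 7.2.1). The safety visit is 90 days after the end of infusion (Section 7.3.1). Assumptions: 3 months = 91 days, 6 months = 183 days, and entry = cycle 1 day 1.

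**Formulas**, for *c* cycles completed without delay:

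- Disconnection day D = 29 + 42 × (c − 1)
- 90-day visit V = D + 90
- Supportive-care gap = max(0, window − D)
- Medication gap = max(0, window − V)

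| Cycles | D | Supportive-care gap, of 91 | Supportive-care gap, of 183 | V | Medication gap, of 183 |
|---|---|---|---|---|---|
| 1 | 29 | 91 − 29 = 62 | 183 − 29 = 154 | 119 | 183 − 119 = 64 |
| 2 | 71 | 91 − 71 = 20 | 183 − 71 = 112 | 161 | 183 − 161 = 22 |
| 3 | 113 | 0 | 183 − 113 = 70 | 203 | 0 |
| 4 | 155 | 0 | 183 − 155 = 28 | 245 | 0 |

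The 1-month count is essentially covered. The medication gap at 3 months is nil when the visit is held on time. For a patient transplanted soon after cycle 1, medication recording closes at the pre-conditioning visit, which can fall shortly after day 29, so both the 3- and the 6-month counts can then be short.

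**How far the gaps depend on dating:**

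- *Full 7-day extension before each further cycle* (D = 29/78/127/176): the supportive-care gap is 154/105/56/7 days at 6 months and 62/13/0/0 at 3 months. The medication gap at 6 months is 64/15/0/0.
- *Entry dated from consent at the start of the 21-day screening window:* every gap falls by up to 21 days. Four cycles: 28 − 21 = 7. Medication: 64 − 21 = 43 and 22 − 21 = 1.
- *Collection run to the end of the six-week cycle* (day 43 instead of day 29): the supportive-care gap falls by up to 14 days. Four cycles: 28 − 14 = 14.
- *Both of the last two* (21 + 14 = 35 days): the 6-month supportive-care gaps become 154 − 35 = 119, 112 − 35 = 77, 70 − 35 = 35 and 0. At 3 months they become 62 − 35 = 27 and 0.

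**Which rule bears on which endpoint.** The Section 7.2 restriction concerns medication, so it affects intravenous antibiotics and antifungals not given for a blinatumomab-related event. Transfusions depend on the supportive-care row. Nothing expressly ends collection of hospital days, but no scheduled item collects them after treatment until the telephone contacts that follow the two-year period.

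**The case against.** The strongest reply is Section 8.2. It names notes review for exactly these three endpoints and sets no cut-off, and since Section 4.3 fixes the windows, the natural reading is that notes are searched to 6 months. This stands in part: a reader might infer that data simply stop, or that use after stopping is counted as zero, and the protocol says neither. But Section 8.2 does not lift the CRF restriction in Section 7.2. Section 6.3 has patients referred from their own hospitals, so later salvage or transplant care may be documented elsewhere, and no request to those hospitals is specified.

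Unplanned admissions are also SAEs, and adverse events are reported to 90 days after the last dose (Sections 9.1 and 9.5). That gives real cover for hospital days at 3 months. It excludes elective admissions and ends near day 119 after one cycle and day 161 after two.

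Section 5.5 sends early stoppers straight into follow-up and speaks of further data, which hints at earlier collection. Yet it places the resource items after the two-year period and only where available. The schedule's concomitant-medication row shows no end, and its notes allow collection at unscheduled visits. The table is damaged by conversion, but the supportive-care row's end point is legible and differs from that of the adverse-event row.

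A reader might also size the loss by giving every cycle 1 non-responder a FLAG-Ida course at the Section 3 figures. The protocol does not support that. Section 5.5 expects four cycles regardless of molecular response, Section 5.9 does not list persistent MRD as a reason to stop, and the inpatient-stay and supportive-care figures in Section 3 are medians.

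**Conclusion.** The point holds as an inconsistency between endpoint windows and scheduled collection. The supportive-care row falls short of the 6-month count by about 154, 112 and 70 days after one, two and three cycles, and still by 119, 77 and 35 days when both later end-of-collection and earlier entry are assumed. The 28-day gap after four cycles may vanish, so it should not be said that completers are necessarily truncated. At 3 months the gap is 62 days after one cycle and 20 after two, and the latter may also close. Medication recording falls short only at 6 months and only after one or two cycles (about 64 and 22 days), except in transplanted patients, for whom it can close earlier.

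Understatement is conditional: it applies to counts that rely on scheduled CRF collection, and it is greatest in early stoppers and transplanted patients. How many hospital days, antibiotic days or units would be missed cannot be derived from the protocol. The primary endpoint and the two-stage decision rule are unaffected.

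**What to change.** Reconcile Sections 4.5, 5.14, 7.2, 7.3 and 8.2 so that hospital days, intravenous antibiotic and antifungal days and blood components are recorded in the CRF to 6 months from one defined entry date. This should apply to every treated patient, regardless of discontinuation, salvage treatment or transplant. State the same window for the notes review in Section 8.2, and exempt these items from the restriction in Section 7.2.

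The contacts largely exist. Section 5.5 already has a six-month visit for patients completing fewer than four cycles, the 90-day visit after four cycles falls beyond 6 months, and Section 7.3.2 already provides contact with transplanted patients or their physicians. Add a records request to outside hospitals. Report the total and, separately, the part before the next anti-leukaemic therapy or conditioning, so that use under blinatumomab can be told apart from use afterwards.

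The cost is protocol and CRF wording and a small amount of extra data collection, with no added procedures. The reported resource use may look less favourable.
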